## **7.0 TRIAL PROCEDURES**

### **7.1 Trial Procedures**

The Trial Flow Chart - Section 6.0 summarizes the trial procedures to be performed at each visit. Individual trial procedures are described in detail below. It may be necessary to perform these procedures at unscheduled time points if deemed clinically necessary by the investigator.

Furthermore, additional evaluations/testing may be deemed necessary by the investigator and or the Sponsor for reasons related to subject safety. In some cases, such evaluation/testing may be potentially sensitive in nature (e.g., HIV, Hepatitis C, etc.), and thus local regulations may require that additional informed consent be obtained from the subject. In these cases, such evaluations/testing will be performed in accordance with those regulations.

#### **7.1.1 Administrative Procedures**

##### **7.1.1.1 Informed Consent**

The investigator or qualified designee must obtain documented consent from each potential subject or each subject's legally acceptable representative prior to participating in a clinical trial or Future Biomedical Research. If there are changes to the subject's status during the trial (e.g., health or age of majority requirements), the investigator or qualified designee must ensure the appropriate consent is in place.

###### **7.1.1.1.1 General Informed Consent**

Consent must be documented by the subject's dated signature or by the subject's legally acceptable representative's dated signature on a consent form along with the dated signature of the person conducting the consent discussion.

A copy of the signed and dated consent form should be given to the subject before participation in the trial.

The initial informed consent form, any subsequent revised written informed consent form and any written information provided to the subject must receive the IRB/ERC's approval/favorable opinion in advance of use. The subject or his/her legally acceptable representative should be informed in a timely manner if new information becomes available that may be relevant to the subject's willingness to continue participation in the trial. The communication of this information will be provided and documented via a revised consent form or addendum to the original consent form that captures the subject's dated signature or by the subject's legally acceptable representative's dated signature.

Specifics about a trial and the trial population will be added to the consent form template at the protocol level.

The informed consent will adhere to IRB/ERC requirements, applicable laws and regulations and Sponsor requirements.

### **7.1.1.1.2 Consent and Collection of Specimens for Future Biomedical Research**

The investigator or qualified designee will explain the Future Biomedical Research consent to the subject, answer all of his/her questions, and obtain written informed consent before performing any procedure related to the Future Biomedical Research sub-trial. A copy of the informed consent will be given to the subject.

### **7.1.1.2 Inclusion/Exclusion Criteria**

All inclusion and exclusion criteria will be reviewed by the investigator or qualified designee to ensure that the subject qualifies for the trial.

### **7.1.1.3 Subject Identification Card**

All subjects will be given a Subject Identification Card identifying them as participants in a research trial. The card will contain trial site contact information (including direct telephone numbers) to be utilized in the event of an emergency. The investigator or qualified designee will provide the subject with a Subject Identification Card immediately after the subject provides written informed consent.

The subject identification card also contains contact information for the emergency unblinding call center so that a health care provider can obtain information about trial medication/vaccination in emergency situations where the investigator is not available.

### **7.1.1.4 Medical History**

A medical history will be obtained by the investigator or qualified designee. Medical history will include all active conditions, and any condition diagnosed within the prior 10 years that are considered clinically significant by the Investigator. Details regarding the disease for which the subject has been enrolled in the trial will be recorded separately and should not be listed in medical history.

### **7.1.1.5 Disease Details**

The Investigator or qualified designee will obtain prior and current details regarding disease status.

### **7.1.1.6 Prior Oncology Treatment History**

The Investigator or qualified designee will record all prior cancer treatments including systemic treatments, radiation and surgeries.

### **7.1.1.7 Prior and Concomitant Medications Review**

#### **7.1.1.7.1 Prior Medications**

The investigator or qualified designee will review prior medication use, including any protocol-specified washout requirement, and record prior medication taken by the subject within 30 days before starting the trial. Treatment for the disease for which the subject has

been enrolled in this trial will be recorded separately and should not be listed in prior medications.

#### **7.1.1.7.2 Concomitant Medications**

The investigator or qualified designee will record medication, if any, taken by the subject during the trial and through the 30-day Safety Follow-up Visit. After the Safety Visit, record all medications related to reportable SAEs and ECIs.

#### **7.1.1.8 Assignment of Screening Number**

All consented subjects will be given a unique screening number that will be used to identify the subject for all procedures that occur prior to randomization or allocation. Each subject will be assigned only one screening number. Screening numbers must not be re-used for different subjects.

Any subject who is screened multiple times will retain the original screening number assigned at the initial screening visit.

Specific details on the screening visit requirements (screening/rescreening) are provided in Section 7.1.5.1.

#### **7.1.1.9 Assignment of Randomization Number**

All eligible subjects will be allocated, by non-random assignment, and will receive a randomization number. The randomization number identifies the subject for all procedures occurring after treatment allocation. While the subjects are being allocated to their treatment, and not 'randomized', this unique number is termed a randomization number throughout the protocol for operational purposes. Allocation of subjects between the two arms will be managed by the Sponsor through an IVRS. Once a randomization number is assigned to a subject, it can never be re-assigned to another subject.

A single subject cannot be assigned more than 1 randomization number.

#### **7.1.1.10 Trial Compliance (Study Drug Administration)**

Interruptions from the protocol specified treatment for  $\geq 28$  days require consultation between the investigator and the Sponsor and written documentation of the collaborative decision on subject management.

All doses of MK-1248 and pembrolizumab will be administered under the supervision of a qualified physician and/or designee experienced in the use of anticancer agents.

Instructions for preparing and administering study drugs will be provided in the Procedure Manual.

## 7.1.2 Clinical Procedures/Assessments

### 7.1.2.1 Adverse Event (AE) Monitoring

The Investigator or qualified designee will assess each subject to evaluate for potential new or worsening AEs as specified in the Trial Flow Chart and more frequently if clinically indicated. Adverse events will be graded according to NCI CTCAE, version 4.0. Toxicities will be characterized in terms of seriousness, causality, toxicity grade and action taken with regard to study treatment.

All AEs of unknown etiology associated with MK-1248 and pembrolizumab exposure should be evaluated to determine if it is possibly an event of clinical interest (ECI) of a potential immunologic etiology (irAE). See Section 5.2.3.2 regarding the identification, evaluation and management of AEs of a potential immunological etiology.

This is a dose escalation trial to establish the MTD of MK-1248 alone and in combination with pembrolizumab; therefore, each dose escalation will be based on the safety and tolerability experienced by subjects at each dose level. The safety and tolerability of each cohort for the DLT evaluation period will be reviewed prior to the start of the next cohort. The Sponsor and the Principal Investigators or Sub-Investigators will review the safety and tolerability of each study treatment, the appropriateness of dose escalation, when each cohort is completed and the next cohort is opened for enrollment. Frequency of these communications will depend on the enrollment of each cohort, as well as any potential new information regarding a safety concern in this trial or other relevant trials.

As a Phase 1 trial, there is no plan for an external safety reviewer. Data from individual subjects will be closely followed on an ongoing basis by the Principal Investigator and the Sponsor.

### 7.1.2.2 Full Physical Examination

The investigator or qualified designee will perform a complete physical exam during the screening period. Clinically significant findings from the screening exam should be recorded as medical history.

A full physical exam should be repeated according to the frequency defined in the Study Flow Chart (Section 6.0). After the first dose of study treatment, new clinically significant abnormal findings should be recorded as AEs.

### 7.1.2.3 Vital Signs and Weight

Vital signs should include temperature, pulse, respiratory rate, blood pressure, and weight at the frequency defined in the Study Flow Chart (Section 6.0).

Height will be obtained at Screening only.

### 7.1.2.4 Electrocardiogram (ECG)

A standard 12-lead ECG will be performed using local standard procedure at Screening, with any clinically significant abnormal findings recorded as medical history.

Additional timepoints for ECGs are according to the Study Flow Chart (Section 6.0). Clinically significant abnormal findings seen on all ECGs performed after Screening should be recorded as AEs.

#### **7.1.2.5 Eastern Cooperative Oncology Group (ECOG) Performance Status**

The investigator or qualified designee will assess the ECOG performance status as the timepoints specified in the Study Flow Chart (Section 6.0).

#### **7.1.2.6 Tumor Imaging**

The initial CT scan or MRI for tumor imaging must be performed within 28 days prior to enrollment, and the site study team must confirm the subject has measurable disease as defined by RECIST version 1.1 to confirm eligibility.

Tumor imaging performed should be repeated every 9 weeks from the first dose of treatment until confirmed disease progression, the start of new anti-cancer therapy, withdrawal of consent, death, or end of the study, whichever is earlier.

The same imaging technique should be performed at each timepoint.

Scans used for tumor measurements may be requested for central review.

#### **7.1.2.7 Response Assessment**

##### **7.1.2.7.1 Immune-related RECIST (irRECIST)**

RECIST 1.1 will be adapted to account for the unique tumor response characteristics seen with treatment with pembrolizumab and MK-2148. Immunotherapeutic agents such as pembrolizumab may produce antitumor effects by potentiating endogenous cancer-specific immune responses. The response patterns seen with such an approach may extend beyond the typical time course of responses seen with cytotoxic agents, and can manifest a clinical response after an initial increase in tumor burden or even the appearance of new lesions. Standard RECIST may not provide an accurate response assessment of immunotherapeutic agents such as pembrolizumab and MK-1248. Immune-related RECIST (irRECIST) is RECIST 1.1 adapted as described below to account for the unique tumor response seen with immuno-therapeutics. irRECIST will be used by site investigators to assess tumor response and progression, and make treatment decisions.

Therefore, RECIST 1.1 will be used with the following adaptations:

If radiologic imaging by local radiology shows initial PD, tumor assessment should be repeated  $\geq 4$  weeks later in order to confirm PD with the option of continuing treatment per below while awaiting radiologic confirmation of progression.

If repeat imaging shows  $<20\%$  increase in tumor burden compared to nadir, stable or improved previous new lesion (if identified as cause for initial PD), and stable/improved non-target disease (if identified as cause for initial PD), PD is not confirmed. Treatment may be continue and subsequently follow regular imaging schedule.

If repeat imaging confirms PD due to any of the scenarios list below, subjects will be discontinued from study therapy and the initial date of Progression recorded as the PD date.

In determining whether or not the tumor burden has increased or decreased, the Investigator should consider all target lesions as well as non-target lesions.

Scenarios where PD is confirmed at repeat imaging:

- Tumor burden increase remains  $\geq 20\%$  and at least 5 mm absolute increase compared to nadir
- Non-target disease resulting in initial PD is worse (qualitative)
- New lesion resulting in initial PD is worse (qualitative)
- Additional new lesion(s) since last evaluation
- Additional new non-target progression since last evaluation

In subjects who have initial evidence of radiological PD, it is at the discretion of the PI whether to continue a subject on study treatment until repeat imaging is obtained. This clinical judgment decision should be based on the subject's overall clinical condition, including performance status, clinical symptoms, and laboratory data. Subjects may receive study treatment while waiting for confirmation of PD if they are clinically stable as defined by the following criteria:

- Absence of symptoms and signs indicating clinically significant progression of disease, including worsening of laboratory values
- No decline in ECOG performance status
- Absence of rapid progression of disease
- Absence of progressive tumor at critical anatomical sites (e.g., cord compression) requiring urgent alternative medical intervention

When feasible, subjects should not be discontinued until progression is confirmed. This allowance to continue treatment despite initial radiologic progression takes into account the observation that some subjects can have a transient tumor flare in the first few months after the start of immunotherapy, but with subsequent disease response. Subjects that are deemed clinically unstable are not required to have repeat imaging for confirmation of progressive disease.

**NOTE:** In subjects who discontinue study therapy without documented disease progression, every effort should be made to continue monitoring their disease status by radiologic imaging every 9 weeks ( $\pm 7$  days) until (1) the start of new anti-cancer treatment, (2) disease progression (3) death, or (4) the end of the study, whichever is earlier.

Confirmation of partial response (PR) and complete response (CR) is required at least 4 weeks after the initial response assessment of PR and CR.

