### 4.2.3 Rationale for Endpoints

#### 4.2.3.1 Efficacy Endpoints

An exploratory endpoint for this trial is to evaluate the anti-tumor activity of MK-1248 and MK-1248 in combination with pembrolizumab in subjects with advanced solid malignancies. Tumor response will be accessed using irRECIST.

Immunotherapeutic agents such as MK-1248 and pembrolizumab may produce antitumor effects by potentiating endogenous cancer-specific immune responses. The response patterns seen with such an approach may extend beyond the typical time course of responses seen with typical cytotoxic agents, and can manifest a clinical response after an initial increase in tumor burden or even the appearance of new lesions. Standard response assessment criteria may not provide a comprehensive response assessment of immunotherapeutic agents such as MK-1248 and pembrolizumab. Therefore, the subject should not be discontinued from treatment unless the initial assessment of PD is confirmed at least 4 weeks later, provided the subject's clinical condition is stable, and irRECIST will thus be used to assess efficacy.

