##### **7.1.8.2 Treatment Period**

Visit requirements are outlined in Section 6.0 - Trial Flow Chart. Specific procedure-related details are provided above in Section 7.1 - Trial Procedures.

After a screening phase of up to 28 days, eligible subject will be assigned to one of 2 Arms and a dose level of MK-1248 by IVRS. In Arms 1 and 2, MK-1248 treatment will be administered on Day 1 of each 21-day cycle for up to a maximum of 4 cycles. In Arm 2, pembrolizumab will be administered on Day 1 of each 21 day cycle for up to 24 months of treatment.

Subjects will be followed until confirmed disease progression, unacceptable adverse event(s), intercurrent illness that prevents further administration of treatment, investigator's decision

to withdraw the subject, subject withdraws consent, pregnancy of the subject, noncompliance with study treatment or procedure requirements, or administrative reasons.

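### Section 7.1.2.7.1: the rule for unconfirmed progression omits two of the five confirmation scenarios, so one repeat scan can be both confirmed and not confirmed

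*Combined protocol and SAP*

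**What the plan says.** Section 7.1.2.7.1 asks for a repeat scan at least 4 weeks after a first radiologic PD and then gives two rules.

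- **Not confirmed.** Burden is less than 20% above nadir, and any new lesion or non-target disease that caused the first PD is stable or improved. The sentence closes "and stable/improved non-target disease (if identified as cause for initial PD), PD is not confirmed". The instruction that follows is "Treatment may be continue and subsequently follow regular imaging schedule".
- **Confirmed.** "If repeat imaging confirms PD due to any of the scenarios list below, subjects will be discontinued from study therapy", with PD dated to the first progression. Five scenarios follow. One of them is "Additional new lesion(s) since last evaluation"; another is additional new non-target progression.

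On what enters the burden judgement, the section says: "In determining whether or not the tumor burden has increased or decreased, the Investigator should consider all target lesions as well as non-target lesions". New lesions are not named there.

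Confirmation matters elsewhere. Section 4.2.3.1 says that, in a stable subject, "the subject should not be discontinued from treatment unless the initial assessment of PD is confirmed at least 4 weeks later". Section 7.1.2.7.1 adds: "When feasible, subjects should not be discontinued until progression is confirmed". Section 5.8 lists confirmed PD twice, once as a reason to leave the trial and once as a reason to stop treatment with continued monitoring allowed. Section 7.1.2.6 runs the 9-weekly imaging until confirmed PD. Section 8.4.3 bases the exploratory endpoints on irRECIST by investigator review and, for best overall response, cites an Appendix 12.6; the table of contents lists appendices only up to 12.5.

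**The concern.** The two rules should be complements, so that every repeat scan falls under exactly one. They are not. Site investigators use this section for treatment decisions as well as for scoring. Two sites reading the same scan could therefore reach different labels, each with protocol text behind it: one keeps the subject on treatment and on regular imaging, the other stops therapy and records the first progression as the PD date.

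Enrollment closed on 31-Mar-2017, but Section 1.0 lets ongoing subjects continue treatment and follows them per protocol, so the rule remains in use.

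**Working it through.** No sample size or error rate is involved. The check sets the two rules side by side, enumerates the outcomes, and traces the timing.

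**1. The rules compared (both from Section 7.1.2.7.1)**

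| Finding at repeat scan | Confirmed if | Not-confirmed sentence requires |
|---|---|---|
| Burden against nadir | at least 20% and at least 5 mm above | less than 20% above; no mm limb |
| Non-target disease behind first PD | worse | stable or improved |
| New lesion behind first PD | worse | stable or improved |
| Additional new lesion | present | nothing |
| Additional new non-target progression | present | nothing |

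**2. A scan that meets both** (illustrative values). Nadir 50 mm. First PD at 62 mm: (62 − 50)/50 = +24%. Repeat at 58 mm: (58 − 50)/50 = +16%, with one additional new lesion. The burden condition holds and no causal lesion is worse, so PD is not confirmed. An additional new lesion is a listed scenario, so PD is confirmed.

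**3. Enumeration.** Take eight yes/no findings: burden at least 20% up; at least 5 mm up; new lesion was a cause; that lesion worse; non-target disease was a cause; that disease worse; additional new lesion; additional new non-target progression. A causal lesion can be worse only if it was a cause, which leaves 3 × 3 × 2⁴ = 144 combinations.

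- Both rules met: 24. All involve an omitted scenario: 16 with an additional new lesion, 8 with additional non-target progression alone. The 8 are a conflict only where that progression has not already been counted in the burden judgement.
- Neither rule met: 4. All have burden at least 20% but less than 5 mm above nadir and nothing else worse. This needs a nadir below 5/0.20 = 25 mm. Example: nadir 20 mm, first PD 26 mm (+30%, +6 mm), repeat 24 mm (+20%, +4 mm). Sections 4.2.3.1 and 7.1.2.7.1 supply a treatment default here (a stable subject stays on until PD is confirmed), so only the scan's label is open.

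These are counts of logical combinations, not patient frequencies.

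**4. Does other text rank the rules?** The paragraphs on clinical stability in 7.1.2.7.1 concern treatment while the repeat scan is awaited, not how it is classified. Section 5.8 uses the term confirmed without defining it. The appendix cited in 8.4.3 is not listed. Nothing sets precedence.

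**5. Treatment timing.** With 21-day cycles on schedule, Day 1 falls at weeks 0, 3, 6, 9, 12, 15 and 18 for Cycles 1 to 7. Regular scans are at weeks 9, 18 and 27. For a first PD at week 9 (window 8 to 10), the earliest repeat is week 13 (12 to 14).

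- Arm 1: MK-1248 is given "on Day 1 of each 21-day cycle for up to a maximum of 4 cycles" (Section 7.1.8.2), so the last dose is at week 9 and none remains at the repeat scan.
- Arm 2: between a repeat at the earliest time and the week-18 scan there is one pembrolizumab dose, Cycle 6 at week 15. The conflict bears on it only if the repeat scan precedes week 15; the protocol gives no latest date for the repeat.

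**6. PD date, same subject.** Under the confirmed reading, PD is dated week 9. Under the other, the result depends on how 8.4.3 treats an unconfirmed PD:

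- it counts as an event: shift 0 weeks;
- it does not count, and the new lesion at week 13 is scored as a fresh first PD (confirmable from week 17): shift 13 − 9 = 4 weeks;
- it does not count, and the lesion is not so scored: a later event or censoring date, so more than 4 weeks.

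**7. After the change.** If not confirmed means that none of the five scenarios is met, the rules are complements: overlaps fall from 24 to 0 and gaps from 4 to 0. Adding only new lesions to the existing sentence would leave 8 overlaps.

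**The case against.** The strongest reply is that a careful reader already knows what to do. The not-confirmed sentence only permits continued treatment, the confirmed sentence is mandatory, and it is triggered by any listed scenario. Stopping therapy breaches neither. That stands as the better reading, but it does not remove the clash: the first sentence also states a classification, which no permission wording softens, and nothing says that the list prevails.

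Several stronger inferences are tempting and are not supported.

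- *Confirmation is a strict gate for stopping.* Section 7.1.2.7.1 leaves continuation before the repeat scan to the investigator and qualifies its advice by feasibility, and 5.8 allows withdrawal on the investigator's decision.
- *Confirmed PD always ends trial participation.* Section 5.8 also lists it under stopping treatment, with monitoring allowed to continue.
- *PFS and duration of response shift by at least 4 weeks.* Section 8.4.3 requires confirmation for responses but does not say that an unconfirmed PD is not an event.
- *The Cycle 6 dose is always at stake.* That holds only for a repeat scan before week 15.
- *Disputed cases cannot be rescored.* Applying either rule to the disputed scan needs only that scan and earlier ones, and 7.1.2.6 and 8.4.3 allow for central review.

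**Conclusion.** The contradiction is real and visible in the text of 7.1.2.7.1, and it is minor. It is firm for an additional new lesion. It is conditional for additional non-target progression, which may already be counted in the burden judgement.

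Its reach is the decision to stop treatment, mainly pembrolizumab in Arm 2, and possibly the PD date for exploratory irRECIST endpoints. For a week-9 first PD the date difference runs from 0 to 4 weeks or more, depending on a convention that 8.4.3 does not state. Effects on best overall response and disease control cannot be sized, because no text says how an unconfirmed PD scan is scored. The timing assumes on-schedule dosing and the earliest permitted repeat. How often such scans occur is unknown. The primary DLT endpoint is unaffected.

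**What to change.** - **Section 7.1.2.7.1.** Replace the conditions of the not-confirmed sentence with one rule: at repeat imaging, PD is confirmed if any of the five listed scenarios is met and not confirmed if none is met. Keep the existing consequences of each outcome.
- **Section 8.4.3.** Refer to this rule for subjects with repeat imaging. State that for clinically unstable subjects, whom 7.1.2.7.1 exempts from repeat imaging, the initial PD counts as the event. Without that exception the reference could leave their progression without a qualifying event.
- **Clerical, separate from the above.** In 8.4.3 replace the citation to the unlisted Appendix 12.6 with Section 7.1.2.7.1.

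The cost is one rewritten sentence, a short addition and a corrected citation. The rewritten sentence also governs continued treatment, so it needs clinical sign-off as protocol text. No new data or visits are needed.
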